GCP	Good Clinical Practice
IB	Investigator's Brochure
IC	Informed Consent
ICMJE	International Committee of Medical Journal Editors
IPMN	Intraductal Papillary Mucinous Neoplasm
METC	Medical research ethics committee (MREC); in Dutch: Medisch Ethische Toetsing Commissie (METC)
MISCAN	Micro-Simulation Screening Analysis
MCA	Mucinous Cystadenoma
MD-IPMN	Main-Duct Intraductal Papillary Mucinous Neoplasm
MPD	Main Pancreatic Duct
MRCP	Magnetic Resonance Cholangiopancreatography
MRI	Magnetic Resonance Imaging
(S)AE	(Serious) Adverse Event
SCA	Serous Cystadenoma
SPN	Solid Pseudopapillary Neoplasm
Sponsor	The sponsor is the party that commissions the organisation or performance of the research, for example a pharmaceutical

company, academic hospital, scientific organisation or investigator. A party that provides funding for a study but does not commission it is not regarded as the sponsor, but referred to as a subsidising party.

SUSAR	Suspected Unexpected Serious Adverse Reaction
UEG	United European Gastroenterology
Wbp	Personal Data Protection Act (in Dutch: Wet Bescherming Persoonsgegevens)
WMO	Medical Research Involving Human Subjects Act (in Dutch: Wet Medisch-wetenschappelijk Onderzoek met Mensen)

SUMMARY

Rationale: Asymptomatic pancreatic cysts are a common finding in this time of elaborate imaging. The malignant potential of these cysts is probably small, but exact data regarding cancer risks are limited. Generally, an intensive surveillance strategy is chosen, driven out of fear to miss one of the most deadly cancers, and based on international recommendations. In 2013, a group of European experts formulated a consensus statement, recommending lifelong follow-up with Magnetic Resonance Imaging (MRI), every 6 to 12 months. This strategy may be justified for some individuals, to timely detect malignant progression, but in the majority of cases, cysts will never progress. Consequently, these patients are likely to undergo lifelong redundant (and costly) investigations.

Objectives: To establish the yield of pancreatic cyst surveillance, based on the recently published European experts consensus statement, and to identify possible alternative, more (cost) effective, surveillance strategies.

Study design: An international multicentre observational cohort study that will run for 10 years. The first analysis will take place after 3 years.

Study population: Patients with a pancreatic cyst - either newly or previously diagnosed - that requires surveillance in the opinion of the treating physician.

Intervention: Cyst surveillance will be performed by the treating physician at the hospital of origin. Based on the recommendations of the consensus statement, patients will be followed every 6 to 12 months by imaging studies (preferably Magnetic Resonance Imaging (MRI/MRCP), with endoscopic ultrasonography (EUS) as an alternative) and determination of serum CA 19.9 levels. Cyst management will remain in the hands of the treating physician. Both treating physicians and participating subjects will provide outcome data, by filling out (on-line) case record forms (CRF) and questionnaires.

Main study parameters/endpoints: Primary endpoints are: the number of patients that reach an indication for surgical cyst resection and the number of patients diagnosed with a malignant cyst (either high-grade dysplasia or carcinoma). Secondary endpoints are: 1. the outcome of patients with an indication for cyst resection; i.e. the number of operated patients, surgical procedures, morbidity, mortality, and cyst recurrence, 2. cyst evolution, in terms of development of symptoms, cyst growth, and other worrisome features, and 3. the perceived burden of surveillance on participants. Other study parameters are; 4. possible risk factors for malignancy, either patient or cyst related, and 5. to build a micro-simulation screening analysis (MISCAN) model, based on the outcome data of this study, in order to determine the optimal strategy for pancreatic cyst surveillance.

Nature and extent of the burden and risks associated with participation, benefit and group relatedness: There will be no risks involved for patients participating in this

study. The follow-up schedule is in accordance with current common practice, and based on recently published surveillance recommendations [1, 2]. The only burden for participating patients may be providing two additional blood samples and filling out an online questionnaire during follow-up. A potential benefit of study participation is a better compliance to the surveillance program.

1. INTRODUCTION AND RATIONALE

Incidental pancreatic cysts are prevalent, in particular in this day and age of cross-sectional imaging[3]. The reported incidence depends on the applied imaging technique and the investigated setting. In CT series of symptomatic patients, the incidence varies from 1 to 3%[4]. In healthy individuals undergoing a screening MRI, we found a pancreatic cyst in 2.4%[5]. An autopsy series by Kimura even reported a prevalence rate of 24%[6].

These cysts form a heterogeneous group of non-neoplastic and neoplastic lesions, with variable pathologic features, clinical presentation, and outcome. Most cysts are (virtually) benign, such as Pseudocysts and Serous Cystadenomas (SCA), and, when asymptomatic, do not require treatment or follow-up. However, some neoplastic cysts have a malignant potential (Mucinous cysts and Intraductal Papillary Mucinous Neoplasms (IPMN)), and require follow-up or even a surgical resection[7, 8]. Unfortunately, to distinguish these pancreatic cysts, especially the smaller ones, is often impossible[9].

A second problem in pancreatic cyst management is that data regarding the natural history and predictive factors for malignant degeneration are virtually lacking.[2, 10]. The literature is biased by highly selected patients series from tertiary referral centres. Sahani reported a 13% risk of malignancy in cysts smaller than 3 cm[2]. In asymptomatic cysts, the reported prevalence of carcinoma varies between 1 and 3%[8]. However, the malignant potential is likely to be much lower, considering the high prevalence of pancreatic cysts and the low incidence of malignant cystic neoplasms. Fitzgerald, for instance, reported a yearly incidence of malignant pancreatic cysts from a state-wide tumour registry in Michigan, USA, of 0.47/100.000[7]. Given the 2.4% incidence of pancreatic cysts on screening MRI's, the calculated malignancy rate would be no more than 0.0002 per year[5].

Because it is impossible to estimate the cancer risk of small pancreatic cysts, treating physicians face a difficult dilemma: to miss a pancreatic carcinoma, or to expose the majority of patients with a benign cystic lesion to redundant investigations, or even unnecessary surgery (with substantial morbidity and mortality). At present, an intensive surveillance strategy is generally chosen, driven out of fear for one of the most deadly cancers.

In 2012, a group of European experts (European study group on cystic tumours of the pancreas) formulated a consensus statement regarding the management of pancreatic cystic neoplasms[1]. These non-evidence based recommendations address the use of imaging techniques, criteria for resection, and a schedule for cyst surveillance. For small,

undifferentiated cysts and side-branch IPMN's, without signs of malignancy, the panel recommends an intensive follow-up strategy, with lifelong surveillance by MRI and determination of serum CA19.9, every 6 to 12 months. Despite the absence of evidence-based data, most likely, this surveillance advice will be widely implemented in clinical practice. Therefore, these recommendations require prompt validation by a prospective cohort study.

Generally, for a surveillance program to be implemented, a yield of 0.2% is required (identifying 5 cases per 1000 subjects followed). To evaluate surveillance strategies, a Micro-simulation SScreening ANalysis (MISCAN) model may be used[11-13]. This widely established mathematical model was developed by the department of Public Health of the Erasmus Medical Center of Rotterdam in 1987. Based on real outcome data from different sources, the model generates a large fictitious population. Not only can it evaluate the subjected screening strategy, but it can also predict the outcome of alternative strategies, in order to optimize future screening. This model was also used to establish the value of colorectal cancer screening in the Netherlands[14].

2. OBJECTIVES

Primary objective

To establish the yield of regular pancreatic cyst surveillance, based on a recently published European experts consensus statement, in terms of identified patients that require cyst resection, diagnosed malignancies, cyst evolution, and the perceived burden for participants.

[figure not shown]
Secondary objective

To identify more (cost) effective surveillance strategies, using acquired information on the natural course of the disease, identified risk factors for malignancy, and calculations from a MISCAN model for cyst surveillance.

3. STUDY DESIGN

The study is designed as a prospective international multicenter cohort study, which will be coordinated by the department of Gastroenterology and Hepatology of the Erasmus University Medical Center of Rotterdam, the Netherlands. The study will run for ten years. Patients with a pancreatic cyst that requires surveillance will be included from September 2014 until August 2023. Follow-up will continue until August 2024. The first analysis will be conducted in September 2017, after three years, to provide data for the MISCAN model.

Figure 1; Study Flowchart

4. STUDY POPULATION

4.1 Population

This study will concern individuals with a pancreatic cyst, either newly or previously diagnosed, that warrant surveillance. Generally, asymptomatic cysts are detected coincidentally, on imaging studies performed for other indications. Based on a reported incidence rate of 2.4%, there are an estimated 200.000 eligible individuals in the Netherlands, mostly over 40 years old [5]. Patients will be recruited in the Netherlands through the network of the 'Dutch Pancreatic Cancer Group' (DPCG) and the 'Dutch Pancreatitis Study Group', and internationally through the members of the 'European study group on cystic tumours of the pancreas'.

4.2 Inclusion criteria

- Individuals with a pancreatic cyst (either newly or previously diagnosed)
- Cyst surveillance is warranted, according to the treating physician
- Age >18
- Informed consent

4.3 Exclusion criteria

- History of chronic pancreatitis
- Suspected pseudocyst (simple, thin walled cyst that developed in the course of acute (necrotising) pancreatitis, as documented by sequential imaging studies)
- Suspected serous cystadenoma (typical microcystic lesion with lobulated outlines and a calcified central scar, and cyst fluid CEA levels < 5 ng/ml)
- Von Hippel-Lindau disease
- Limited life expectancy (< 2 years)

4.4 Sample size calculation

In total, we aim to include 5000 patients during the study period of 10 years, of which 250 patients per year will be included in the Netherlands. This will provide over a 1000 patient years after three years, even in the case of expected loss to follow-up (15% of

patients included in the first year, 10% of those included in the second year, and 5% included in the third year). Internationally, depending on the number of cooperating centres throughout Europe, we expect to include between 250 and 500 patients yearly.

5. TREATMENT OF SUBJECTS

5.1 Diagnostic work-up before inclusion

The goal of the diagnostic work-up is to characterize the cyst and to rule out malignancy. This work-up should have taken place no more than 6 months prior to inclusion. A high quality cross-sectional imaging study, either Computed Tomography (CT) or Magnetic Resonance Imaging (MRCP) should always be performed. (based on the consensus statement, MRCP is preferred). In addition, in new cysts (diagnosed less than 6 months prior to inclusion), serum CA 19.9 should be determined. New cysts over 1 cm in size should also be evaluated by endoscopic ultrasonography (EUS), with fine needle aspiration (FNA), if technically feasible.

5.2 Inclusion and cyst surveillance

If cyst follow-up is warranted according to the treating physician, and in- and exclusion criteria are met, a patient is eligible for the study. Cyst surveillance will take place at the hospital of origin, and will be coordinated by the treating physician. The advised surveillance strategy is based on the consensus statement, and consists of imaging studies (MRCP or EUS), every 6 to 12 months, and determination of serum CA 19.9 (Figure 2, see also paragraph 6.3, study procedures)[1].

5.3 Cyst management during follow-up

During follow-up, the treating physician is responsible for patient management and decision-making. If follow-up parameters change during follow-up, the decision for a more elaborate diagnostic work-up, surgery, or an intensified follow-up schedule is at the discretion of the treating physician.

5.4 Data collection

Treating physicians will be asked to fill out an online case record form regarding the choice and outcome of the imaging studies, serum and cyst fluid analysis, and the clinical condition of the patient. Patients will fill out questionnaires regarding their quality-of-life and the burden of cyst surveillance.

Any cyst related event will be recorded (i.e. changes in follow-up parameters or strategy, additional imaging studies, reaching an indication for cyst resection, the decision for or against treatment (with motivations), surgical procedures, complications of surgery, pathological outcome). If conservative management is chosen although resection criteria

are met, the argumentation for this decision will be noted. Cyst follow-up will be continued in this group and the subsequent outcome will be monitored. Data collection will continue until August 2024. The database will not only be used for data analysis, but will also automatically generate reminders to the treating physician, regarding follow-up dates.

6. METHODS

6.1 Study endpoints

6.1.1 Main study endpoints

- The number of patients who reach an indication for pancreatic cyst resection, based on the criteria of the consensus statement (specified in Table I).
- The number of patients, diagnosed with a malignant cyst (either high-grade dysplasia or carcinoma).

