12. ADDENDUM

Figure 2; Flowchart of pancreatic cyst surveillance, based on the recommendations of the consensus statement by the European study group on cystic tumours of the pancreas[1].

[figure not shown]

Table I: Resection criteria, as recommended in the consensus statement by the European study group on cystic tumours of the pancreas [1].

Resection criteria for cystic neoplasms of the pancreas		

 - 1. Cysts \geq 4 cm in size - 2. Cysts diagnosed as 
 - Mucinous Cystic Neoplasm (MCN) - Main-duct Intraductal Papillary Mucinous Neoplasm (MD-IPMN)), - Solid Pseudopapillary Neoplasm (SPN) - 3. Presence of risk factors* for malignancy (\geq1 absolute or \geq 2 relative) 		
* Risk factors	Absolute criteria	Relative criteria
Cyst related	
 - Mural nodules - Dilatation Main Pancreatic Duct (MPD) $>$ 6 mm - Eggshell calcifications 	
 - Significant growth
Patient related	
 - Jaundice - Acute pancreatitis - Diabetes 	
 - Elevated serum CA 19.9 - Epigastric pain - Weight loss

Table II: Types of pancreatic cyst resection

Surgical procedure
Pylorus preserving pancreaticoduodenectomy or classic Whipple procedure
Duodenum preserving pancreatic head resection (Beger/Frey's procedure)
Distal pancreatectomy with/without splenectomy
Central pancreatectomy
Other

Table III: Predicted morbidity and mortality after surgical resection

Morbidity (Major complications)	Mortality
Pancreatic fistula Anastomotic leak Postoperative bleed Other complications requiring re-laparotomy	30- and 90-day postoperative mortality

Table IV: Potential risk factors of malignancy; patient and cyst related

Patient Characteristics	Cyst Morphology	Cyst Fluid
Age (years)	Number of cysts (Single/Multiple)	Presence Mucin
Sex (M/F)	Cyst size (bidirectional)	Cytology
Body Mass Index (BMI)	Cyst growth	CA 19.9
History of pancreatitis	Location (head, neck, body, or tail)	CEA
History of pancreatic cyst/cancer	Micro- or macrocystic pattern	Amylase
History of pancreatic surgery	Uni- or multilocular	
Family history pancreatic cancer	Internal septa (if yes, enhancing?)	
Family history of breast and/or colon cancer	Cyst wall (thick > 2 mm/thin < 2 mm)	
Symptoms of steatorrhea	Solid components (if yes; enhancing?)	
Diabetes	Calcifications (if yes; central/peripheral)	

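### Both primary endpoints count events however they were found, so the figure reported as surveillance yield will be cohort incidence that mixes surveillance-detected cases with interval and lapsed cases

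*Protocol*

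**What the plan says.** Section 2 of the protocol states the primary objective: "To establish the yield of regular pancreatic cyst surveillance", measured "in terms of identified patients that require cyst resection, diagnosed malignancies, cyst evolution, and the perceived burden for participants".

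Section 6.1.1 gives two primary endpoints. The first is "The number of patients who reach an indication for pancreatic cyst resection, based on the criteria of the consensus statement", with those criteria set out in Table I. The second is "The number of patients, diagnosed with a malignant cyst (either high-grade dysplasia or carcinoma". The summary repeats both. Neither places a condition on how, when or at what kind of examination the event came to light.

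Table I (section 12) allows an indication through "Presence of risk factors* for malignancy", met by one absolute or two relative factors. The patient-related factors include jaundice, acute pancreatitis, epigastric pain and weight loss.

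On the programme itself, section 5.2 says: "The advised surveillance strategy is based on the consensus statement, and consists of imaging studies (MRCP or EUS), every 6 to 12 months". Section 5.3 leaves management to the treating physician.

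On recording, section 5.4 says: "Any cyst related event will be recorded (i.e. changes in follow-up parameters or strategy, additional imaging studies, reaching an indication for cyst resection", followed by the treatment decision, surgery, complications and pathology. What prompted the examination that led to the event is not on that list. Section 8.1 breaks results down by cyst type, new or previous diagnosis, and EUS or MRCP, but not by mode of detection.

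**The concern.** The yield of a surveillance programme is ordinarily understood as what the programme finds. A count of all indications and all malignant cysts in the cohort also includes what it did not find: cancers that declare themselves between examinations, and cases in patients who had stopped attending. If these are pooled, a failure of surveillance raises the reported figure just as a success does.

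The figure has uses beyond description. Section 8 feeds the three-year outcome data into the MISCAN model and uses them to decide on follow-up frequency after five years. Section 6.1.3 wants the model to design more efficient strategies. Comparing intervals depends on knowing which cases the examinations found and which they missed.

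**Working it through.** The protocol states no figure for the share of events found outside surveillance, so there is no number of its own to reproduce. The check has two parts.

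**1. How events score under the protocol's own definitions**

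| Course | Endpoint 1 (indication) | Endpoint 2 (malignant cyst) |
|---|---|---|
| Mural nodule seen at a scheduled MRCP, carcinoma at resection | 1 | 1 |
| Jaundice between two scheduled examinations, carcinoma confirmed | 1 | 1 |
| Acute pancreatitis after surveillance has lapsed, carcinoma confirmed | 1 | 1 |

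The three rows score the same, because Table I accepts each presentation and section 6.1.1 adds no condition. (The extracted Table I appears to list nodules, jaundice and acute pancreatitis as absolute criteria; column alignment is uncertain. Endpoint 2 does not depend on it.)

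The second and third rows are foreseeable. Section 6.3 recommends one-year intervals for most patients. Section 4.4 expects losses of 15%, 10% and 5% in the first three yearly entry cohorts. At 250 Dutch patients a year that is 250 × (0.15 + 0.10 + 0.05) = 75 of 750, or 10%. Loss to follow-up is not the same as lapsed surveillance with a later event, so this shows only that incomplete attendance is anticipated. It is not an estimate of f.

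**2. Size of the difference**

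Let A be all events and S those found at a scheduled surveillance examination, over the same denominator. Let f = (A − S)/A. Then S = A(1 − f), and the reported figure divided by surveillance-detected yield is A/S = 1/(1 − f).

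The values of f below are assumptions. For scale, take the two readings of the benchmark yield in section 1, applied to the planned 5000 patients: 0.2% is 10 cases, and 5 per 1000 is 25 cases (0.5%). Those two readings disagree with each other, which is a separate matter.

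| Assumed f | 1/(1 − f) | Surveillance-detected if all-event figure is 0.2% | If all-event figure is 0.5% |
|---|---|---|---|
| 10% | 1.11 | 0.18% (9 of 5000) | 0.45% |
| 20% | 1.25 | 0.16% (8 of 5000) | 0.40% |
| 30% | 1.43 | 0.14% (7 of 5000) | 0.35% |
| 50% | 2.00 | 0.10% (5 of 5000) | 0.25% |

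The share f may well differ between the two endpoints.

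**The case against.** **The protocol does not define yield as what scheduled examinations find.** Section 2 describes it through patients needing resection, malignancies, cyst evolution and burden, and the endpoints follow that list. This stands as far as it goes: there is no literal contradiction, and nowhere does the protocol say in words that interval cancers count as yield. That follows from reading the objective together with the endpoints. But section 2 speaks of identified patients under regular surveillance, and that sense of detection is not carried into section 6.1.1.

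**Much of the information is collected.** Section 5.4 records imaging choice and outcome, clinical condition and additional imaging; the database holds follow-up dates for reminders; section 6.1.2 makes development of symptoms a secondary endpoint. The eCRF is not shown, so the absence of a trigger field is not established, and an analysis plan could classify recorded events. This also stands in part. Reconstruction may be possible, but nothing in the protocol requires it. A symptom noted at diagnosis does not show what prompted the examination: weight loss may be recorded at a routine visit.

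**Stronger readings are tempting.** A reader might infer that a programme missing every cancer and one detecting every cancer would give the same second endpoint. The documents do not support this. That endpoint includes high-grade dysplasia, a tissue diagnosis that normally follows detection and resection, and cancers not apparent by the end of follow-up in August 2024 would go uncounted. A reader might also infer that MISCAN could not be informed about test sensitivity. That is too strong: section 1 says the model draws on data from different sources, and section 8 does not restrict its input to undivided totals.

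**The benchmark is only background.** Section 8 tests nothing against the required yield in section 1. This is correct; it is used above for scale only.

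**Conclusion.** The concern holds in a limited form. As defined, the primary endpoints measure cohort incidence of indications and malignant cysts. Presented as the yield of surveillance, they overstate the surveillance-detected part by 1/(1 − f). The direction is certain for any f above zero. The size cannot be derived from the protocol, and the range 1.11 to 2.00 rests wholly on an assumed f of 10% to 50%.

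The endpoints are incomplete for the stated objective rather than invalid. The all-events count remains a legitimate quantity and is needed for the risk-factor analysis in section 8.2. The change should be made because it is cheap and lets the study answer its own question; it does not rank as a must-fix.

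**What to change.** - **Section 6.1.1:** report each primary event by mode of detection: (a) found at a scheduled surveillance examination; (b) found between examinations, through symptoms or incidentally; (c) found after surveillance had lapsed, with the margin for lapse fixed in advance for analysis. Define surveillance yield as (a), report (b) and (c) separately, and keep the all-events count as cohort incidence and for the risk-factor analysis. Classify by what prompted the examination, not by whether symptoms were present.
- **Section 5.4:** list the trigger of the examination that led to the event as a recorded item, if the eCRF does not already hold it. Prospective recording is preferable to later attribution.
- **Section 8:** supply the split to MISCAN.

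The cost is at most one eCRF item per event, a wording change and a simple classification rule. The rule needs some care because physicians set the actual schedules. The stated yield will be less favourable. Patient care does not change.

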8.2 Univariate analysis

For the primary endpoints, univariate comparisons will be conducted, to identify individual patient and cyst risk factors for malignancy (Table IV). As primary potential risk factors are considered; 1. Cyst size, 2. Cyst growth, 3. Mural nodules/solid components, 4. increased serum CA 19.9, 5. Pancreatic duct dilatation, and 6. Patient age. Survival analysis techniques and Cox regression with time-dependent recurrent covariates measures will be applied to assess significance.

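### High-grade dysplasia in the malignancy endpoint is confirmed mainly after resection, and five of the six tested risk factors are resection criteria, so their hazard ratios on the composite are likely biased upward

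*Protocol*

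**What the plan says.** The malignancy endpoint in Protocol 6.1.1 is a count: "The number of patients, diagnosed with a malignant cyst (either high-grade dysplasia or carcinoma". No verification standard common to all patients is stated.

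Section 6.3 has surgical specimens sent for central pathology revision. The only other tissue route is cytology on fine needle aspirate (FNA), which 5.1 foresees at the work-up of new cysts over 1 cm. Surveillance itself is imaging plus serum CA 19.9.

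Section 5.3 says that, when follow-up parameters change, further work-up, "surgery, or an intensified follow-up schedule is at the discretion of the treating physician". Table I in the Addendum gives the consensus resection criteria: size of 4 cm or more, certain cyst diagnoses, and "Presence of risk factors* for malignancy", meaning at least one absolute or two relative factors. These include "Mural nodules", "Dilatation Main Pancreatic Duct (MPD" above 6 mm) and "Significant growth".

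Section 8.2 lists the primary candidate risk factors as "1. Cyst size, 2. Cyst growth, 3. Mural nodules/solid components, 4. increased serum CA 19.9, 5. Pancreatic duct dilatation, and 6. Patient age", and says that "Cox regression with time-dependent recurrent covariates measures will be applied to assess significance".

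**The concern.** The test that reveals high-grade dysplasia is applied mainly to patients selected by the factors whose association with malignancy is being tested. Dysplasia in a patient without those features is likely to stay unseen and to enter the Cox model as event-free time, at least until it progresses. The model then reads a difference in verification as a difference in hazard.

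Identifying risk factors in order to design better surveillance is a stated aim (section 2 and 6.1.3). The introduction describes the consensus recommendations as not evidence-based and in need of validation. A bias toward the existing criteria would make the cohort partly confirm them by construction, and a larger sample does not reduce it.

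**Working it through.** The protocol states no figure on this point, so there is nothing to reproduce. The check has a textual part and a numerical part, and the numerical part rests wholly on assumed inputs.

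**1. Overlap of tested factors and resection criteria**

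| Factor in 8.2 | Place in Table I |
|---|---|
| Cyst size | criterion by itself (4 cm or more) |
| Cyst growth | relative factor |
| Mural nodules/solid components | nodules: absolute factor |
| Serum CA 19.9 | relative factor |
| Pancreatic duct dilatation | absolute factor (above 6 mm) |
| Patient age | not listed |

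Five of six overlap. The argument does not reach age.

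**2. Closed form for the composite**

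Let h be the dysplasia share of malignancies, and v1 and v0 the probabilities that dysplasia is verified with and without the factor. Carcinoma is taken as always detected. With a true ratio of 1:

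observed ratio = [h·v1 + (1−h)] / [h·v0 + (1−h)]

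- h = 0.5, v1 = 0.5, v0 = 0.05: (0.25 + 0.5)/(0.025 + 0.5) = 1.43
- low end, h = 0.3, v1 = 0.3, v0 = 0.10: 0.79/0.73 = 1.08
- high end, h = 0.7, v1 = 0.7, v0 = 0.05: 0.79/0.335 = 2.36

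For dysplasia alone (h = 1) the ratio is v1/v0: 0.5/0.10 = 5, 0.7/0.05 = 14, 0.8/0.02 = 40. At h = 0.5, the 0.7 versus 0.05 case gives only (0.35 + 0.5)/(0.025 + 0.5) = 1.62 on the composite.

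**3. Simulation**

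Assumptions:
- The factor is present in 10% at entry and acquired by 3% a year.
- Dysplasia arises at 0.5% a year and progresses to carcinoma at 10% a year.
- Dysplasia is found only at resection. Carcinoma is found at resection or with 90% probability at each annual visit.
- Resected patients leave the risk set. Follow-up is eight years.
- The estimate is a year-stratified Mantel-Haenszel rate ratio, standing in for Cox.

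With a true ratio of 1:

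| Annual resection, factor vs no factor | Composite, same-visit covariate | Composite, previous-visit covariate | Carcinoma only, previous-visit covariate |
|---|---|---|---|
| 10% vs 10% | 1.02 | 1.01 | 1.00 |
| 10% vs 5% | 1.39 | 1.38 | 1.02 |
| 10% vs 2% | 1.74 | 1.69 | 0.97 |
| 30% vs 2% | 3.93 | 3.57 | 0.99 |

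With 5000 patients, follow-up spread over 1 to 10 years, about 48 to 55 events and a two-sided 0.05 test, the composite false-positive rate is 4.8% for 10% vs 10%, 23% for 10% vs 5% and 98% for 30% vs 2%.

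**4. Covariate timing**

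The third column shows that using the previous visit's covariate leaves most of the bias. Timing matters more if the feature can be a consequence of the cancer. If carcinoma produces the feature with an assumed 50% probability a year, 30% vs 2% resection gives 12.3 same-visit and 3.9 previous-visit on the composite. For carcinoma alone it gives 11.3 and 1.5.

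**5. Can the carcinoma-only model err the other way?**

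Yes. In the simulation with a true ratio of 2 and 30% vs 2% resection, the composite gives 5.80 and carcinoma alone 1.46 (same-visit), against 1.83 if every dysplasia were seen. Not all of that shortfall comes from resection, since carcinoma alone gives 1.61 even at 10% vs 10%.

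A second set of assumptions has dysplasia at 0.4% a year, progression at 12% a year, 30% vs 2% resection, ten years and a true ratio of 3. Carcinoma alone then gives:
- 2.98 if patients are censored at resection and resection is unrelated to dysplasia given the factor;
- 1.9 if they are censored but cysts with dysplasia are resected twice as readily;
- 0.68 if resected patients stay in the risk set.

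**The case against.** **Size.** A reader might infer a 5- to 40-fold inflation from the ratio of verification rates. That holds for dysplasia alone. The endpoint in 6.1.1 includes carcinoma, which dilutes the bias to the smaller figures above.

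**Selection is incomplete.** Table I also lists cyst diagnoses, jaundice, pancreatitis, diabetes, pain and weight loss. Growth and CA 19.9 are only relative factors, surgery is discretionary, and FNA cytology may find some cases without resection. All this stands. It weakens the link between tested factors and verification but does not remove it.

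**Data and reach.** Section 5.4 already records pathological outcome, reasons for or against surgery, and the course of unoperated patients who meet the criteria. Risk factors are an other endpoint in 6.1.3, and the main endpoint is a count. This also stands, and it makes the remedy cheap. But following patients who meet criteria does not verify dysplasia in those who never meet them.

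**Covariate timing.** A reader might infer that 8.2 prescribes same-visit covariates. It is silent on timing, which may be left to the statistical analysis plan, so the silence is not an error.

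**MISCAN.** A reader might infer that the biased hazard ratios feed the MISCAN model. Section 8 says the first report is descriptive and that those outcome data are the input. Nothing says the Cox estimates enter it.

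**The remedy has its own bias.** Resection can remove dysplasia before it progresses, mostly in patients with the features. This stands. A rule accepting only factors on which both models agree could therefore discard true predictors.

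**Conclusion.** The point holds in a limited form and is a cheap improvement. The endpoint definition, the resection criteria, the list of tested factors and the Cox model are all fixed in the protocol, and together they make upward bias likely for five of the six factors on the composite endpoint. Nothing in the protocol corrects it.

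The documents do not allow the size to be computed. About 1.1 to 2.4 (closed form) and 1.4 to 3.9 (simulation) under no true effect show what is possible. They depend on the assumed dysplasia share and verification or resection rates, and on carcinoma being found largely regardless of the factor. With equal resection in both groups the bias disappears. The count of diagnosed patients can stand as defined.

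**What to change.** Keep the composite for the count. In 6.1.1 and 8.2:

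1. Report carcinoma and high-grade dysplasia separately.
2. Report the proportion of patients with histological verification by each risk factor.
3. Add a carcinoma-only risk-factor model as a required companion analysis, with patients censored at resection.
4. State that the composite model may overstate the five factors that are also resection criteria, and that the carcinoma-only model may understate them because resection can remove dysplasia before it progresses. Interpret the two together as a range, without requiring agreement.
5. Optionally, add a sensitivity analysis using covariates from before the diagnostic visit. It guards against features that are consequences of the cancer, but does not remove the verification bias.

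The cost is some wording and one more model on data already collected. The downside is fewer events and wider intervals for carcinoma alone, possibly too few to pass the rule in 8.3 of more than 30 events for multivariate analysis. In that case the companion model would stay univariate.
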